4.2. Participant Dispositions

A listing of study disposition for all randomized participants will be provided at the final database lock. Summaries of study disposition and study drug disposition for all randomized participants will be provided by planned study treatment at the final database lock.

4.3. Primary Endpoints Analysis

For submission of Study GPHL to the US FDA to support the registration of tirzepatide for chronic weight management, both primary efficacy assessments will be guided by the treatment regimen estimand conducted using the FAS. Assessment of the primary objectives will be conducted with hybrid imputation of missing data (see Section 4.3.2.3).

For other regulatory agencies, publications and other purposes, the assessment of efficacy objectives may be guided by the efficacy estimand using the EAS.

4.3.1. Definition of Endpoint(s)

The primary efficacy measure will be percent change in body weight AND percentage of participants who achieve $\geq 5\%$ body weight reduction from randomization at 72 weeks.

The percent change in body weight is defined as:

$$(\text{postbaseline body weight [kg]} - \text{baseline body weight [kg]}) / \text{baseline body weight [kg]} * 100.$$

4.3.2. Main Analytical Approach

4.3.2.1. The Analysis Related to the Treatment Regimen Estimand

The analysis related to treatment regimen estimand will be conducted using data in the FAS.

The analysis for the mean percent change in body weight will be conducted utilizing ANCOVA. The response variable for the ANCOVA model will be percent change in body weight from randomization at 72 weeks. A logistic regression model will be used for the analysis of the percentage of participants achieving at least 5% body weight reduction obtained at the 72-week visit. Both models will include terms of treatment group, country/pooled country, sex, and type of AHM (significant weight gain, significant weight loss, weight neutral and others) used at randomization as fixed effects and baseline body weight as a covariate. The ANCOVA analysis will be conducted with hybrid imputation of missing body weight at 72 weeks (see Section 4.3.2.3 for details) and statistical inference over multiple imputation of missing data guided by Rubin (1987). As for the logistic regression, missing body weight data at 72 weeks will be imputed first based on imputation method specified in Section 4.3.2.3, then the continuous measurements will be categorized into status of achieving at least 5% body weight reduction (Yes or No).

With the aid of the ANCOVA model, 2-sided 95% CI for mean percent change in body weight from baseline to the 72-week visit between tirzepatide 10 mg and placebo, as well as tirzepatide 15 mg and placebo will be derived.

With the aid of the logistic regression model, 2-sided 95% CI and odds ratio for percentage of participants achieving at least 5% body weight reduction from baseline to the 72-week visit between tirzepatide 10 mg and placebo, as well as tirzepatide 15 mg and placebo will be derived.

4.3.2.2. The Analysis Related to the Efficacy Estimand

The analysis related to efficacy estimand will be conducted utilizing data in the EAS.

For the mean percent body weight change from randomization, a MMRM will be conducted. REML will be used to obtain model parameter estimates and the Kenward-Roger option will be used to estimate the denominator degrees of freedom. The response variable of MMRM will be the percent change in body weight from baseline values obtained at each scheduled post baseline visit.

For the percentage of participants achieving at least 5% body weight reduction from randomization over time, a logistic regression model will be used with the response variable of achieving at least 5% body weight reduction (Yes or No) at 72-week visit, with missing value imputed using the predicted value from MMRM analysis followed by dichotomization.

For MMRM the independent variables of analysis model are treatment group, visit, treatment-by-visit interaction, stratification factors (type of AHM used at randomization, sex, and country/pooled country) as fixed effects, and baseline body weight as a covariate. An unstructured covariance structure will model relationship of within-patient errors. If this model fails to converge, the following variance covariance structures will be tested in order until convergence is achieved:

- heterogeneous Toeplitz
- heterogeneous first order autoregressive
- heterogeneous compound symmetry
- Toeplitz
- first order autoregressive, and
- compound symmetry.

The first covariance structure that converges will be used.

With the aid of the MMRM analysis, 2-sided 95% CIs for mean percent change in body weight from randomization to the 72-week visit for tirzepatide 10 mg and 15 mg compared to placebo will be derived and summarized. The resulting least squares mean (LSM) estimates of mean percent change in body weight from baseline will be plotted by visit and by study treatment.

With the aid of the logistic regression model, 2-sided 95% CI and odds ratio for percentage of participants achieving at least 5% body weight reduction from baseline to the 72-week visit between tirzepatide 10 mg and placebo, as well as tirzepatide 15 mg and placebo will be derived.

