For all other purposes, the primary efficacy assessment will be guided by the “efficacy” estimand, which represents efficacy prior to discontinuation of study drug without confounding effects of antihyperglycemic rescue therapy, and conducted using the EAS. The primary analysis model will be a MMRM for body weight percent change over time and longitudinal logistic regression for proportion of participants achieving at least 5% body weight reduction over time. The response variable of MMRM will be the percent change in body weight from randomization values obtained at each scheduled postbaseline visit. The response variable of longitudinal logistic regression will be the proportion of participants achieving at least 5% body weight reduction at each scheduled post-randomization visit. The independent variables of both analysis models are treatment group (tirzepatide 10 mg, tirzepatide 15 mg, and placebo), visit, and treatment-by-visit interaction, stratification factors, and baseline body weight as covariate. An unstructured covariance structure will model relationship of within-patient errors. The Kenward-Roger approximation will be used to estimate denominator degrees of freedom.

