SS	(1.2) Treatment-Emergent Abnormal Labs ^a , Vital Signs, and ECGs.	Baseline will include all scheduled and unscheduled measurements during the baseline period (Visit 1 to Visit 3)	Postbaseline will be defined as measurements after Visit 3. All scheduled and unscheduled measurements will be included.
SS	(1.3) Change from Last Baseline to Week xx and to Last Postbaseline for Labs ^a , Vital Signs, and ECGs.	The last scheduled and unscheduled non-missing assessment recorded during the baseline period defined above (1.2).	Postbaseline will be defined as above (1.2). Only scheduled visits will be included. The ED visits are considered scheduled visits.

Abbreviations: ECGs = electrocardiogram; ED = early discontinuation; SS = Safety Analysis Set.

^a Immunogenicity related analysis is specified in Section 4.6.5.5.

For the primary and key secondary efficacy endpoint analyses subject to type 1 error rate control, data for participants with missing values at the 72-week visit will be imputed based on the method described in Section 4.3.2.3. Otherwise, missing values will not be explicitly imputed except for the parameters with only 1 postbaseline measure during the analysis period per schedule of activity, where last observation carried forward (LOCF) approach will be applied to impute the endpoint when early discontinuation measure is available.

End of study participation for a participant will be the earliest of date of death, date of withdrawal from further participation in the study, or date of safety follow-up visit (Visit 801). For participants considered to be lost-to-follow-up, end of study participation will be the date of lost-to-follow-up reported by the investigator. Participant data included in the database after the last date of study participation (including safety follow-up period) will be excluded from statistical analysis.

Statistical treatment comparisons will only be performed between tirzepatide and placebo. Since the trial is not adequately powered to detect differences among tirzepatide doses, comparisons among tirzepatide doses will not be performed unless otherwise specified.

Statistical summaries and results of statistical analyses will be displayed in the following order: placebo, tirzepatide 10 mg, tirzepatide 15 mg, and pooled tirzepatide (all doses combined) if necessary.

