4.3.2.3. Methods for Hybrid Imputations

For efficacy analyses relative to “treatment-regimen” estimand, missing values resulting from ICEs will be handled as follows:

- Category 1: for missing data solely due to exceptional circumstances, such as pandemic or natural disasters (after other reasons for missing data are ruled out), the analysis will consider the missing data as missing at random. The missing data will be imputed using all nonmissing data of the primary outcome measurement from the same treatment arm.

- Category 2: for missing data due to all other ICEs, missing data will be imputed based on retrieved dropouts in the same treatment arm, defined as observed primary outcome measurements from participants in the same treatment group, who had their efficacy assessed after early discontinuation of the study drug. In cases where there are not enough retrieved dropouts to provide a reliable imputation model (eg, the model implemented by the SAS program does not converge), an alternative multiple imputation method with reference to the placebo group (that is, placebo multiple imputation) will be used.

In cases where placebo multiple imputation method is used for missing data imputation in Category 2 due to not enough retrieved dropouts, the missing data in Category 1 will also be imputed using all nonmissing data of the primary outcome measurement from the placebo group.

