4.4. Secondary Endpoint(s)/Estimands(s) Analysis

4.4.1. Key Secondary Analyses Subject to Type 1 Error Rate Control

Table GPHL.4.2. Key Secondary Measures (Controlled for Type 1 Error)

Objectives	Relative to the efficacy measure:	Analysis conducted in a manner similar to	Additional Information
Tirzepatide 10 mg and/or 15 mg is superior to placebo:	Percentage of participants achieving body weight reduction $\geq 10\%$, $\geq 15\%$ and $\geq 20\%$ at 72 weeks	logistic model in Section 4.3.2.1 for treatment-regimen estimand and logistic model in Section 4.3.2.2 for efficacy estimand	
	Mean change in HbA1c (%) from randomization at 72 weeks	ANCOVA model in Section 4.3.2.1 for treatment-regimen estimand and MMRM model in Section 4.3.2.2 for efficacy estimand, with baseline HbA1c value to replace baseline body weight as an additional covariate.	LSM estimates will be plotted by treatment through 72 weeks.
	Percentage of participants achieving target value of HbA1c $< 7\%$, $\leq 6.5\%$ and $< 5.7\%$ at 72 weeks	logistic model in Section 4.3.2.1 for treatment-regimen estimand and logistic model in Section 4.3.2.2 for efficacy estimand, with baseline HbA1c value to replace baseline body weight as an additional covariate.	
	Mean change in waist circumference (cm) from randomization at 72 weeks	ANCOVA model in Section 4.3.2.1 for treatment-regimen estimand and MMRM model in Section 4.3.2.2 for efficacy estimand, with baseline waist circumference to replace baseline body weight as an additional covariate.	LSM estimates will be plotted by treatment through 72 weeks.
	Mean change in fasting glucose (mg/dL) from randomization at 72 weeks	ANCOVA model in Section 4.3.2.1 for treatment-regimen estimand and MMRM model in Section 4.3.2.2 for efficacy estimand	Baseline fasting glucose will be used a covariate and baseline HbA1c group ($\leq 8.5\%$, $> 8.5\%$) will be used as a fixed effect. LSM estimates will be plotted by treatment through 72 weeks.
Tirzepatide (all doses combined) is superior to placebo:	Mean change in triglycerides, HDL-cholesterol, and non-HDL-cholesterol from randomization at 72 weeks	ANCOVA model in Section 4.3.2.1 for treatment-regimen estimand and MMRM model in Section 4.3.2.2 for efficacy estimand, with baseline lipids value in place of baseline body weight as a covariate.	Estimated means will be plotted by treatment through 72 weeks. Log transformation will be adopted for lipid parameters.

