- Conduct logistic regression model on the subgroup with terms of treatment group, country/pooled country, sex, and type of AHM used at randomization as fixed effects, and baseline body weight as covariate. Missing body weight measurement at 72 weeks will be imputed by the predicted value from MMRM model on the subgroup aforementioned, then the continuous measurements will be dichotomized into status of achieving at least 5% body weight reduction (Yes or No). For the subgroup analysis on the type of AHM used at randomization, variable type of AHM used at randomization will be removed from logistic regression model as a fixed effect.
- Conduct logistic regression model with terms of treatment group, subgroup, treatment-by-subgroup-interaction, country/pooled country, sex, and type of AHM used at randomization as fixed effects, and baseline body weight as a covariate. Missing body weight measurement at 72 weeks will be imputed by the predicted value from full MMRM model aforementioned, then the continuous measurements will be dichotomized into status of achieving at least 5% body weight reduction (Yes or No). For the subgroup analysis on the type of AHM used at randomization, variable type of AHM used at randomization will be removed from logistic regression model as a fixed effect.

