The sample size determination assumes that evaluation of superiority of tirzepatide 10 mg and tirzepatide 15 mg to placebo will be conducted in parallel, each at a 2-sided significance level of 0.025 using a 2-sample t-test. Additionally, a difference of at least 11% mean body weight percentage reduction from randomization at 72 weeks for tirzepatide 10 mg and/or tirzepatide 15 mg compared to placebo, a common SD of 10%, and a dropout rate of 25% are assumed for statistical power calculations. Under the assumptions above, randomizing 900 participants in a 1:1:1 ratio to tirzepatide 10 mg (300), tirzepatide 15 mg (300), and placebo (300) provides more than 90% power to demonstrate superiority of each tirzepatide dose to placebo.

The chosen sample size and randomization ratio also provides >90% power to establish superiority of 10-mg tirzepatide and 15-mg tirzepatide dose to placebo in terms of proportion of participants achieving at least 5% body weight reduction at 72 weeks, conducted in parallel using a Chi-square test, each at a 2-sided significance level of 0.025, assuming 25% placebo treated participants and 90% tirzepatide-treated participants achieving the goal and a dropout rate of 25%.

6. Supporting Documentation

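### Under the efficacy estimand, dichotomising one MMRM prediction for each missing Week-72 weight inflates the ≥5% and ≥10% odds ratios and gives confidence intervals that cover too rarely

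*SAP*

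**What the plan says.** SAP Section 4.3.2.2 fits a logistic model to Week-72 response, "with missing value imputed using the predicted value from MMRM analysis followed by dichotomization", and takes the odds ratio and 95% CI from it. It mentions no residual draw, repeated imputation or pooling. It also does not say whether the prediction uses the participant's own earlier weights or only the fixed effects.

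The method reaches further than the co-primary:
- Table GPHL.4.2 (Section 4.4.1) assigns the ≥10%, ≥15% and ≥20% endpoints to the "logistic model in Section 4.3.2.1 for treatment-regimen estimand and logistic model in Section 4.3.2.2 for efficacy estimand". The HbA1c targets follow the same pattern.
- For subgroups, Section 4.7.2.1 says: "Missing body weight measurement at 72 weeks will be imputed by the predicted value from MMRM model on the subgroup aforementioned".

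Multiple imputation with Rubin's rules appears only for the treatment-regimen estimand (Section 4.3.2.1). Section 4.3.2.3 opens by limiting itself to that estimand, for which "missing values resulting from ICEs will be handled as follows". The sensitivity analyses in Section 4.3.2.4 have the same limit. Section 4.1, however, says of all endpoints under type 1 error control that "data for participants with missing values at the 72-week visit will be imputed based on the method described in Section 4.3.2.3", without separating the estimands.

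Protocol Section 9.4.3.1 planned a "longitudinal logistic regression for proportion of participants achieving at least 5% body weight reduction over time". SAP Section 4.9 does not list the change.

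On use, Section 4.3 says that for other agencies, publications and other purposes "the assessment of efficacy objectives may be guided by the efficacy estimand using the EAS".

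**The concern.** The variance of a predicted value is smaller than the variance of the outcome it stands for. If the prediction has correlation r with the outcome, its SD is r times the outcome SD. A threshold cut then gives the wrong response probability: above 50% it is pushed up, below 50% it is pushed down. The plan's own rates at ≥5% (25% placebo, 90% tirzepatide; SAP Section 5) lie on opposite sides of 50%, so the two arms move apart and the odds ratio rises. Because each filled value counts as an observation, the standard error is also too small.

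The odds ratio is the declared population-level summary for the responder endpoints (Section 1.1.2.1), so the reported effect itself is at stake. The efficacy analysis set discards weights after last dose plus 7 days (Table GPHL.3.1). Weights collected after discontinuation, including at Visit 99, therefore cannot reduce the missingness.

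**Working it through.** **Inputs from SAP Section 5.** 300 per arm; two-sided 0.025 per dose; difference 11 points; SD 10; responders 25% and 90% at ≥5%; dropout 25%. The plan's power claim reproduces: with 300 × 0.75 = 225 per arm, power exceeds 0.999 for both co-primaries, consistent with the stated >90%.

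**Assumed, because the documents do not give them.** Visit correlations, dropout timing, arm means, and data missing at random. The plan's two sets of assumptions do not fit one normal model: 25% on placebo with a difference of 11 and SD 10 implies Φ(−0.674 + 1.1) = Φ(0.426) ≈ 66% on tirzepatide, not 90%. Both sets were therefore run.

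**Closed form.** If the true response rate is Φ(z), filled participants respond at rate Φ(z/r). For 90% and 25%, z = 1.282 and −0.674:

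| r | tirzepatide, filled | placebo, filled |
|---|---|---|
| 0.5 | 99.5% | 8.9% |
| 0.7 | 96.6% | 16.8% |
| 0.9 | 92.3% | 22.7% |

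With 25% missing and r = 0.7:
- Tirzepatide: 0.75 × 90% + 0.25 × 96.6% = 91.65%.
- Placebo: 0.75 × 25% + 0.25 × 16.8% = 22.95%.
- Odds ratio: (0.9165/0.0835) ÷ (0.2295/0.7705) ≈ 37, against a true 9 ÷ (1/3) = 27.

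With an arm-mean fill, every missing tirzepatide participant becomes a responder and every missing placebo participant a non-responder. The rates are then 92.5% and 18.75%, and the odds ratio is (0.925/0.075) ÷ (0.1875/0.8125) ≈ 53.

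**Simulation.** 300 per arm, 10 post-baseline weight visits, uniform monotone dropout, unstructured MMRM, unadjusted odds ratios, 1500 trials per setting. The Week 60–72 correlation was 0.90 or 0.95. Week 72 then correlates 0.55–0.90 or 0.75–0.95 with the last on-treatment visit. Entries are odds ratio (95% CI coverage) with a conditional prediction:

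| Setting | True OR | corr. 0.90 | corr. 0.95 |
|---|---|---|---|
| 90%/25%, ≥5%, 25% missing | 27.0 | 38.6 (72%) | 33.1 (87%) |
| Same, 10% missing | 27.0 | 31.4 (92%) | 29.8 (94%) |
| SD 10, means −13/−2, ≥5%, 25% missing | 6.0 | 7.5 (78%) | 6.7 (90%) |
| Same, ≥10% | 6.0 | 7.5 (77%) | 6.7 (90%) |

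- In the first row the responder rates become 91.7% and 22.6% (corr. 0.90), or 91.0% and 23.8% (corr. 0.95).
- Arm-mean fill in that setting gives about 55, coverage 21–22%.
- Multiple imputation from the same model gives 27.2–27.8, coverage about 97%.
- At 25% missing the bias is 0.6–1.4 standard errors, while the standard error is only about 7–12% too small. Bias is the main cause of the lost coverage.

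**Second simulation.** Dropout was weighted to early visits and the logistic model was covariate-adjusted. The 25%/90% rates and the difference of 11 were met together by SD 11/(1.282 + 0.674) ≈ 5.6.
- 25% missing: the ≥5% odds ratio goes from 27.1 to 42.2 (coverage 56%), and ≥10% from 29.8 to 45.4 (74%).
- SD 10, assumed means −3 and −14, 25% missing: inflation factors 1.35 and 1.39, coverage 67% and 58%.
- Multiple imputation, over all scenarios run at these two thresholds: factors 0.98–1.04, coverage 94–99%.

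**No true effect at ≥5%, conditional prediction.** In the first simulation the 0.025 test rejected 3.3–4.7% of the time with 25% missing in both arms, and 3.6–5.5% with 10% against 30% missing. Multiple imputation rejected 1.3–1.9%.

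**The case against.** **Size.** The magnitude rests on inputs the plan does not supply. The 25% is a sample-size dropout rate; no figure is planned for weights missing after last dose plus 7 days. With 5–10% missing, or a visit correlation of 0.97, inflation can be only 2–10% with near-nominal coverage. The two simulations differ for the same headline case (72–87% against 56%). The odds-ratio scale also magnifies the shift near 90%: a 65-point difference in rates becomes only about 67–69 points. All of this stands. It limits the size, not the direction at ≥5% and ≥10% with a conditional prediction, where every scenario run showed inflation.

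**The ≥10% threshold.** This depends on tirzepatide exceeding 10% loss, which Protocol Section 4.3 expects for both doses. At an assumed mean of −9 the conditional prediction still inflated the odds ratio (3.2 to 3.7). If the mean falls short of 10%, an arm-mean prediction can give little bias or even a slight reduction (factors 0.89–1.17).

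**Higher thresholds.** The direction is unsettled. At ≥15%, conditional prediction gave 6.8 to 7.5–8.2 in the first simulation, but a factor of 0.93 in the single run of the second. No direction is claimed at ≥15%, at ≥20% or for the HbA1c targets; the last were not simulated.

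**Documentation.** Section 4.3.2.3 limits its own scope, so Sections 4.1 and 4.3.2.2 can be read together with the specific text governing. Protocol Section 9.4.1 lets a change of method be described in the SAP or the study report, and the new method is described. What remains is unclear wording in Section 4.1 and a change listed and justified nowhere in the SAP.

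**Conclusion.** The concern holds. A single MMRM prediction followed by dichotomisation is a biased way to estimate responder odds ratios, and no other part of the SAP repairs it for the efficacy estimand. At ≥5% and ≥10% with about 25% missing and a conditional prediction, the first simulation puts the inflation at roughly 1.1 to 1.4 times, and the second, with earlier dropout, at up to about 1.5 to 1.6 times. Coverage falls clearly below 95%. At 10% missing the effect is modest. An arm-mean prediction, which the text does not rule out, roughly doubles the odds ratio when the threshold lies between the arm means.

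Not affected are the superiority verdict at the planned effect (rejection was 100% in simulation), the continuous MMRM co-primary, and the treatment-regimen analysis used for primary disclosure and the FDA. What suffers is the size and precision of responder effects wherever the efficacy estimand is reported. The mechanism and direction at ≥5% and ≥10% are firm; the exact figures depend on the assumed correlations, dropout timing, missing fraction and arm means. This should be corrected, but it does not threaten the trial's main conclusion.

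**What to change.** - In Section 4.3.2.2, and by reference in Sections 4.4.1 and 4.7.2.1, draw multiple imputations of the missing Week-72 value from the MMRM distribution conditional on the participant's earlier on-treatment values. Each draw should carry parameter uncertainty and a residual term. Dichotomise each completed data set, fit the logistic model and combine by Rubin's rules.
- In Section 4.1, state which imputation applies to which estimand, so that it agrees with Sections 4.3.2.2 and 4.3.2.3.
- In Section 4.9, list the replacement of the protocol's longitudinal logistic regression and give the reason.

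The cost is SAP wording and a modest amount of programming. No new data or participants are needed.

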4. EQ-5D-5L

The mental health questionnaires (Patient Health Questionnaire-9 [PHQ-9], Columbia-Suicide Severity Rating Scale [C-SSRS], and Self-Harm Form) should be completed after the assessment for AEs.

Participants will receive an initial consultation with a dietician, or equivalent qualified delegate, according to local standards. Lifestyle goals for caloric intake and physical activity will be set (Section 5.3).

Following randomization, study site personnel will demonstrate use of the autoinjector (also referred to as single-dose pen) using the provided demonstration device and observe the study participant inject the first dose of tirzepatide or placebo. The date, time, and location of the first dose of study drug will be recorded on the electronic case report form (eCRF). Beginning at randomization, all participants will receive study drug according to the randomized treatment arm for the duration of the 72-week treatment period including a dose escalation period of up to 20 weeks.

Treatment Period (End of Visit 3 to Visit 21)

During the treatment period, office visits will occur monthly through 24 weeks and then every 12 weeks thereafter, to 72 weeks. The participant should be fasting for all office visits.

Telephone visits will occur at 4-week intervals between the office visits starting at Week 28.

Office visit procedures should be conducted according to the SoA (Section 1.3), and will include:

- weight, waist circumference, and vital signs measurements
- laboratory testing
- administration of PROs questionnaires
- collection of AEs, product complaints (PCs), and concomitant medications
- review of SMBG values and hypoglycemic events collected in the diary
- Mental Health questionnaires
- review of participant diary information (to include reinforcement and compliance assessments for study drug administration and lifestyle goals)
- study drug and supplies dispensing

Patient-reported outcomes questionnaires should be administered as early as possible in the visit, as per Suggested Visit Structure (Section 10.8). Preferred administration order is the same as Randomization visit.

Mental Health questionnaires should be completed after the assessment of AEs.

Lifestyle consultations continue at Weeks 4, 8, 12, and then every 12 weeks thereafter, to Week 72. Study drug and injection supplies will be returned per the SoA (Section 1.3) and according to local requirements. New supplies will be dispensed as needed.

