- Full MMRM model: treatment group, visit, subgroup, treatment-by-visit-interaction, treatment-by-subgroup-interaction, subgroup-by-visit-interaction, treatment-visit-subgroup-interaction, country/pooled country, sex, and type of AHM used at randomization as fixed effects, and baseline body weight as a covariate. Variance-covariance structure for within-patient errors will be same as Section 4.3.2.2. For the subgroup analysis on the type of AHM used at randomization, the variable type of AHM used at randomization will be removed from MMRM model as a fixed effect.

For the percentage of participants achieving at least 5% body weight reduction at 72 weeks, for each subgroup analyses aforementioned, 2 models will be conducted as described below.

Treatment regimen estimand

- Conduct logistic regression model on the subgroup with terms of treatment group, country/pooled country, sex, and type of AHM used at randomization as fixed effects, and baseline body weight as covariate. Missing body weight measurement at 72 weeks will be imputed using the imputation method described in Section 4.3.2.3, then the continuous measurements will be dichotomized into status of achieving at least 5% body weight reduction (Yes or No). For the subgroup analysis on the type of AHM used at randomization, variable type of AHM used at randomization will be removed from logistic regression model as a fixed effect.

- Conduct logistic regression model with terms of treatment group, subgroup, treatment-by-subgroup-interaction, country/pooled country, sex, and type of AHM used at randomization as fixed effects, and baseline body weight as a covariate. Missing body weight measurement at 72 weeks will be imputed using the imputation method described in Section 4.3.2.3, then the continuous measurements will be dichotomized into status of achieving at least 5% body weight reduction (Yes or No). For the subgroup analysis on the type of AHM used at randomization, variable type of AHM used at randomization will be removed from logistic regression model as a fixed effect.

Efficacy estimand

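### The efficacy-estimand MMRM fits one baseline slope across all visits; a baseline-by-visit term would recover a little Week 72 precision wherever that slope changes over time

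*SAP*

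**What the plan says.** SAP 4.3.2.2 lists the fixed effects of the efficacy-estimand model: "For MMRM the independent variables of analysis model are treatment group, visit, treatment-by-visit interaction, stratification factors". Baseline weight follows as a covariate, and the covariance is unstructured: "as fixed effects, and baseline body weight as a covariate. An unstructured covariance structure will model relationship of within-patient errors". Protocol 9.4.3.1 has the same terms: "visit, and treatment-by-visit interaction, stratification factors, and baseline body weight as covariate". Treatment is the only term crossed with visit. The response is "The response variable of MMRM will be the percent change in body weight from baseline values obtained at each scheduled post baseline visit".

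The subgroup MMRM in SAP 4.7.2.1 spells out its visit interactions ("treatment-by-visit-interaction, treatment-by-subgroup-interaction, subgroup-by-visit-interaction, treatment-visit-subgroup-interaction"). A visit interaction that is not listed in 4.3.2.2 is therefore most naturally read as absent.

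Table GPHL.4.2 reuses this MMRM under the efficacy estimand for HbA1c, waist circumference, fasting glucose, lipids and SBP. Table GPHL.4.3 reuses it for weight in kg, BMI, 7-point SMBG, fasting insulin, DBP and the remaining lipids.

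The treatment-regimen analysis in SAP 4.3.2.1 has a different form: "The response variable for the ANCOVA model will be percent change in body weight from randomization at 72 weeks". Its baseline slope is specific to Week 72 by construction.

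**The concern.** The baseline covariate is there to remove between-participant variation from the Week 72 comparison. With one slope for all visits, the fitted value is a generalised-least-squares average over visits. Early visits have small variance and so carry most of the weight. If the baseline association grows as weight is lost, the fitted slope reflects the early weeks, and the Week 72 estimate gets little of the adjustment that the data could give.

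What is at stake is precision at Week 72 under the efficacy estimand. The same model also supplies the values used to fill in missing responder status ("with missing value imputed using the predicted value from MMRM analysis followed by dichotomization"), so it is fair to ask whether the slope matters there too.

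**Working it through.** **1. The plan's own figure.** SAP section 5 assumes an 11-point difference, SD 10, 25% dropout, 300 per arm and two-sided alpha 0.025 per dose. That leaves 300 × 0.75 = 225 per arm. SE = 10 × √(2/225) = 0.943 and 11/0.943 = 11.7, against a critical value of 2.24. Power is about 1.000, which agrees with the stated figure of more than 90%. For responders (25% v 90%), SE = √[(0.1875 + 0.09)/225] = 0.035 and 0.65/0.035 is above 18. Power is again about 1.000.

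**2. Visits.** Protocol 4.1.1.2.2 says "office visits will occur monthly through 24 weeks and then every 12 weeks thereafter, to 72 weeks". Weight is therefore taken at Weeks 4, 8, 12, 16, 20, 24, 36, 48, 60 and 72, which is ten post-baseline visits.

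**3. Percent weight change.** Let b be the vector of true slopes (points per SD of baseline weight) and Ω the residual covariance over visits. In large samples the common slope tends to

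b_c = 1′Ω⁻¹b / 1′Ω⁻¹1,

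and the Week 72 variance is inflated by

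1 + (b₇₂ − b_c)² / s₇₂², where b₇₂ = 10r and s₇₂² = 100(1 − r²).

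Assumptions not in the documents:
- r is the correlation of baseline weight with Week 72 percent change, from 0 to 0.3.
- The slope grows in proportion to weight change, on a linear or a saturating time course.
- The visit SD rises with the share f of the Week 72 change as 2 + 8f points, reaching the planned 10 at Week 72.
- The correlation between adjacent visits is 0.90 to 0.97.

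| r | Week 72 slope | Fitted common slope | SE, common slope | SE, slope by visit | Excess SE |
|---|---|---|---|---|---|
| 0 | 0 | 0 | 0.943 | 0.943 | 0% |
| 0.1 | 1.0 | −0.13 to 0.07 | 0.942–0.944 | 0.938 | 0.4–0.7% |
| 0.2 | 2.0 | −0.27 to 0.15 | 0.940–0.948 | 0.924 | 1.8–2.7% |
| 0.3 | 3.0 | −0.41 to 0.23 | 0.936–0.955 | 0.899 | 4–6% |

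Example at r = 0.2, upper end: s₇₂² = 96; 1 + (2.0 + 0.269)²/96 = 1.0536; √1.0536 = 1.0265. The by-visit SE is √(2 × 96/225) = 0.924, and 0.924 × 1.0265 = 0.948.

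**4. Simulation check.** This used 900 participants, ten visits, about 25% monotone missing-at-random dropout, mean change −3% on placebo and −14% on tirzepatide, adjacent correlation 0.97, and 25 replicates per scenario.
- The ratio of model SEs (common slope to slope by visit) was 1.000, 1.005, 1.023 and 1.054 for r = 0, 0.1, 0.2 and 0.3.
- Treatment differences (common v by visit) were −10.84 v −10.84, −11.41 v −11.37, −11.13 v −11.10 and −11.16 v −11.13.
- Misclassified responders among those missing at Week 72 were 12.6–13.6% v 12.7–13.8% when predictions condition on observed visits, and 27.0–28.3% v 27.1–28.9% when they use fixed effects only.

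**5. Weight change in kg.** Suppose percent change is unrelated to baseline weight. The slope of kg change on baseline weight is then the mean proportional change at that visit, which grows over time. Assume mean losses of 14%, 14% and 3% (the planned 11-point gap), mean baseline 100 kg, residual SD 10% (so 10 kg), an exponential time course with visit SDs growing in proportion to the loss, and adjacent correlation 0.90–0.97. The pooled slope runs from −0.016 kg/kg at Week 4 to −(14 + 14 + 3)/300 = −0.103 at Week 72. The fitted common slope is −0.007 to −0.002, so the gap is 0.096 to 0.101.

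Variance inflation = (gap × baseline SD)²/10²:
- 15 kg: (0.096 × 15)²/100 = 2%
- 20 kg: 3.7% to 4.1%
- 25 kg: (0.101 × 25)²/100 = 6%

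That is roughly 1–3% of the SE. With the SD pattern of step 3 and correlation 0.97 the inflation would be somewhat above this range, so 2–6% is illustrative.

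**The case against.** The strongest reply is that nothing here is an error. The protocol and SAP agree, the model is prespecified and valid for the randomised comparison, and a larger SE is conservative. Percent change is already divided by baseline weight, so its remaining slope may be close to flat, in which case the cost is nil. The documents give no baseline slope at any visit. All of this stands. It limits the point to efficiency and makes it conditional. It does not dispose of it, because weight in kg goes through the same model. If percent loss grows over visits, the slope cannot be flat for both percent and kg change.

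A reader might go further and infer that the common slope puts dropouts in the wrong responder category. The simulation does not support that: misclassification was essentially the same with and without the interaction. The larger contrast there (about 13% v 28%) comes from whether the predicted value conditions on the participant's observed visits. SAP 4.3.2.2 leaves that open. It is a separate question that the interaction would not settle.

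A reader might also carry the point over to the analysis for primary disclosure and the FDA. That analysis is a Week 72 ANCOVA with its own imputation and does not use this MMRM.

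Nor do the weight figures transfer directly to every endpoint. HbA1c, for example, is first measured after baseline at Week 12, and lipids at fewer visits. The cost for those endpoints was not computed.

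**Conclusion.** The point holds as a small, conditional loss of efficiency confined to the efficacy estimand. As written, one baseline slope serves all post-baseline visits, and where the true slope changes over time the Week 72 comparison is under-adjusted. For percent weight change the excess SE is 0% at r = 0, under 1% at r = 0.1, about 2–3% at r = 0.2 and 4–6% at r = 0.3. For kg change the variance excess is about 2–6% at a baseline SD of 15–25 kg.

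These sizes rest on assumed correlations, time courses and baseline SDs; only the 11-point difference, SD 10, dropout and sample size come from the plan. The simulation is small, so the SE figures rest on the large-sample formula and model SEs rather than empirical SDs. Power stays at about 1.000, the treatment difference is not materially biased, and no harm to responder classification was shown.

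**What to change.** In SAP 4.3.2.2, add a baseline-by-visit interaction to the MMRM for percent change in body weight. Carry it, with each endpoint's own baseline, to the other endpoints in Tables GPHL.4.2 and GPHL.4.3 that are analysed by MMRM under the efficacy estimand. Record the added term in SAP 4.9, since Protocol 9.4.3.1 lists the model without it, and make the change before unblinding.

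The cost is one model term. For weight, ten slopes replace one, so there are 9 extra parameters against about 900 participants, and fewer for endpoints measured less often. No extra data are needed and no covariance parameters are added. Where the slope is flat the term costs essentially nothing (SE ratio 1.000 at r = 0).
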